3.3 Study Design

This is a randomized, single-center, double-blind, placebo-controlled, parallel-group study in which healthy male subjects will be randomly assigned to one of the following treatments:

- Treatment 1: moxidectin 4 mg (n = 10)
- Treatment 2: moxidectin 8 mg (n = 10)
- Treatment 3: moxidectin 16 mg (n = 10)
- Treatment 4: moxidectin 24 mg (n = 10)
- Treatment 5: moxidectin 36 mg (n = 10)
- Treatment 6: matching placebo (n = 10)

Subjects will be screened for eligibility up to 28 days before randomization. Subjects who meet all of the inclusion and none of the exclusion criteria will be admitted to the CRU on Day -1 (not less than 12 hours before scheduled dosing). Subjects will remain in the CRU for at least 72 hours after dosing and will return to the CRU for further assessment on Days 8, 15, and 22, and Week 12. At Week 8, subjects will be contacted via telephone for recording of AEs and concomitant medication use.

Randomized subjects will be assigned unique subject numbers in sequential order based on their order of qualification. Randomization will take place before dosing on Day 1, with equal random assignment to each treatment. Subjects are considered as enrolled once randomized.

The duration of participation in the study for each subject will be up to approximately 112 days, including Screening.

For purposes of statistical analysis, this study is divided into 2 study periods:

- Period 1: Commences at Screening and will finish on Day 22. The study blind will be maintained during this study period. After the last subject has completed the study through Period 1, the blind will be broken and the data from Period 1 will be analyzed.
- Period 2: Runs from Day 23 to Week 12. Data from Period 2 will be analyzed after all subjects have completed the study through Week 12. Data for some subjects may be collected during Period 2 after the blind has been broken.

The overall schedule of events is provided in Table 1 and the Period 1, Day -1 to Day 4 schedule of events is provided in Table 2.

Table 1. Overall Schedule of Events

Assessment	Screening D-28 to D-2	Period 1									Period 2										
		D-1	Baseline D1 (Predose)	D1	D2	D3	D4	D8	D15	D22	W8	W12 ^f									
Outpatient visit	X	Refer to Table 2: Schedule of Events for Period 1 (Day -1 to Day 4)									X	X	X		X						
Informed consent	X																				
Telephone call																				X	
Inclusion/exclusion criteria review	X																				
Demographic information	X																				
Medical and medication history	X																				
Physical examination ^a	X															X	X	X			X
Vital signs ^b	X																	X			X
Height	X																				
Body weight	X																				
Calculation of body mass index	X																				
Hematology, serum chemistry, and urinalysis ^c	X																	X			X
Urine drug screen	X																				
Serology	X																				
Safety 12-lead electrocardiogram ^d	X																	X			X
Continuous 12-lead electrocardiogram																					
PK blood sample collection ^e																X	X	X			
PK feces sample collection																					
PK urine sample collection																					
Randomization																					
Study drug administration																					
Adverse events	X																				
Concomitant medications	X																				

Abbreviations: D, day; PK, pharmacokinetic; W, week.

- a. A full physical examination will be performed at Screening. At all subsequent time points, a symptom-based physical examination (informed by concurrent conditions, signs and symptoms, and adverse events reported) will be performed.
- b. Vital signs (supine blood pressure, heart rate, respiratory rate, and oral body temperature) will be measured after the subject has rested for approximately 5 minutes.
- c. Blood samples for hematology and serum chemistry and a urine sample for urinalysis will be collected at Screening, on Days -1, 2, 3, 4, 22, and Week 12. Subjects must fast for at least 8 hours before clinical laboratory testing.
- d. Standard 12-lead safety electrocardiograms will be performed after the subject has been supine for approximately 10 minutes. At each relevant time point, safety 12-lead electrocardiograms will be performed before blood collection.
- e. Blood samples will be collected for PK assessments at Baseline (0 hour; within 15 minutes before dosing) and at 0.5, 1, 2, 3, 4*, 5, 6, 8, 12*, 24*, 36*, 48, 60*, and 72 hours after dosing, and on Days 8, 15, and 22. (* Planned time points for analysis of moxidectin metabolite concentrations, 8-mg cohort only)
- f. If a subject discontinues from the study or is withdrawn, the investigator will notify the sponsor and, when possible, will perform the following procedures: vital sign measurements; safety 12-lead electrocardiogram; symptom-based physical examination; collection of adverse events; and clinical laboratory evaluation (including hematology, serum chemistry, and urinalysis).

Table 2. Schedule of Events for Period 1 (Day –1 to Day 4)

Assessment	Period 1																
	Day –1	Day 1 (Predose)	Day 1										Day 2		Day 3		Day 4
Hour relative to dosing	≤-24		0	0.5	1	2	3	4	5	6	8	12	24	36	48	60	72
Admission to unit	X																
Discharge from unit																	X
Confirmation of eligibility	X																
Physical examination ^a	X							X				X	X		X		X
Body weight	X																
Hematology, serum chemistry, and urinalysis	X												X		X		X
Urine drug screen	X																
Randomization		X															
Commence fasting ^b	X																
Study drug administration ^b			X														
Consumption of a standardized meal								X									
Safety 12-lead electrocardiogram ^c				X	X	X	X	X	X	X	X	X	X		X		X
Continuous 12-lead electrocardiogram ^d			←-----X-----→														
Vital signs ^e		X															X
PK blood sample collection ^f		X		X	X	X	X	X	X	X	X	X	X	X	X	X	X
PK feces sample collection ^g		X	←-----X-----→										←--X--→		←-----X-----→		
PK urine sample collection ^h		X	←-----X-----→										←--X--→		←-----X-----→		
Adverse events	X	X	←-----X-----→														
Concomitant medications	X	X	←-----X-----→														

Abbreviation: PK, pharmacokinetic.

- a. A full physical examination will be performed at Screening. At all subsequent time points, a symptom-based physical examination (informed by concurrent conditions, signs and symptoms, and adverse events reported) will be performed.
- b. On Day –1, subjects will begin fasting as instructed and water can be taken ad libitum. On Day 1, study drug administration (moxidectin or placebo) will occur after an overnight fast of at least 10 hours. Study drug will be administered with at least 240 milliliters of water. No food will be allowed for 4 hours after dosing; however, water can be taken ad libitum.
- c. Standard 12-lead safety electrocardiograms (ECGs) will be performed after the subject has been supine for approximately 10 minutes. At each relevant time point, safety 12-lead ECGs will be performed before blood collection.
- d. Continuous 12-lead ECG data will be obtained using a Mortara continuous 12-lead digital ECG recorder, with triplicate 10-second ECG recordings (approximately 1 minute apart) extracted at the following time points: Baseline (before dosing on Day 1) and at 0.5, 1, 2, 3, 4, 5, 6, 8, 12, 24, 36, 48, 60, and 72 hours after dosing.
- e. Vital signs (supine blood pressure, heart rate, respiratory rate, and oral body temperature) will be measured after the subject has rested for approximately 5 minutes.
- f. Blood samples will be collected for PK assessments at Baseline (0 hour; within 15 minutes before dosing) and at 0.5, 1, 2, 3, 4*, 5, 6, 8, 12*, 24*, 36*, 48, 60*, and 72 hours after dosing, and on Days 8, 15, and 22. (* Planned time points for analysis of moxidectin metabolite concentrations, 8-mg cohort only)

- g. Feces samples will be collected for PK assessments before dosing (single predose collection*) and each bowel motion during confinement in the clinical research unit. Samples will be pooled at the central laboratory for intervals of 0 to 24, 24 to 48, and 48 to 72 hours after dosing (up to 4 samples). (* Feces specimens [the whole bowel movement] may be collected by subjects [at home] within 2 days of submitting them to study staff on Day -1. Collection instructions will be provided at Screening.)
- h. Urine samples will be collected for PK assessments before dosing (single predose collection; first void sample in the morning is acceptable and volume recording is not required) and for pooled intervals of 0 to 24, 24 to 48, and 48 to 72 hours after dosing (4 samples).

3.4 Unblinding Procedures

The study will be double-blind and the blind will be maintained through the use of blinding envelopes held by the dispensing pharmacist. All randomization information will be secured and housed in a locked storage area, accessible only by the randomization personnel, the assigned pharmacist, and his or her verifier(s). Neither the subjects nor CRU staff administering the study drug will know the study drug being administered. To maintain the blind, each subject will receive 18 matching tablets. The placebo tablets will be matched in appearance to the active study drug, and will contain the same excipients as moxidectin tablets but will not contain moxidectin.

The study drug blind will not be broken by the investigator or designee unless information concerning the study drug is necessary for the medical treatment of the subject. The blinding envelopes containing randomization information for each subject will be sent to the CRU. The sponsor or medical monitor must be notified immediately if the study drug blind is broken. The date, time, and reason that the blind was broken will be recorded in the source documents.

For Period 1, which commences at Screening, the study blind will be maintained for all personnel through Day 22. Once all subjects complete Period 1, the database will be locked for all data to Day 22. The database will not yet include study data from Week 8 or 12. To allow primary analysis after completion of Day 22, the study blind will be broken for data management, the study statistician, primary and validation programmers, the Cardiac Safety Expert (Mason Cardiac Safety Consultation), the PK vendor (Nuventra Pharma Sciences, Inc), medical writers, and the sponsor for purposes of data analysis and review. All other personnel, including those conducting subject procedures and assessments, will remain blinded.

The study will then be unblinded for all other personnel including the clinic and other biometrics roles after all subjects complete the Week 12 assessments and the data collected in Period 2 is locked.

3.5 Interim Analyses

The primary analysis will be performed once all subjects have completed Day 22. An additional safety supplement will be provided once all subjects complete Week 12. In addition, concentrations of moxidectin in urine and feces and moxidectin metabolites in plasma and urine and associated PK parameters will not be included in the primary analyses after Day 22; however, those data will be analyzed after Period 2 and included in the safety supplement. No interim analysis and early termination is planned. However, the overall safety pattern will be monitored closely and the study may be discontinued for valid scientific or administrative reasons.

Only 1 set of datasets, tables, listings, and graphs are outlined in this SAP. The intent is to summarize all available data after Period 1, and then, rather than producing 2 sets of datasets and tables (1 for each period), the datasets and tables will be reproduced with the

additional data added from Period 2 to replace the existing datasets and TLFs from Period 1.

4 GENERAL STATISTICAL CONSIDERATIONS

All analyses described in this plan are considered a priori analyses in that they have been defined prior to breaking the blind. All other analyses, if any, designed subsequent to breaking the blind will be considered post hoc analyses and will be applied as exploratory methodology. All post hoc analyses will be identified as such in the clinical study report.

All statistical tests will be tested at $\alpha=0.05$, 2-sided significance level, unless otherwise stated. Descriptive statistics for continuous variables will include number of subjects (n), mean, standard deviation (SD), median, minimum, and maximum, unless otherwise noted. Confidence intervals (CIs) will be presented where appropriate. Descriptive statistics for categorical variables will consist of frequency and percentage.

All analyses will be conducted with SAS[®] Version 9.4 or later using procedures appropriate for the particular analysis.

5 ANALYSIS POPULATIONS

5.1 Safety Population

The safety population will include all subjects who receive at least 1 dose of study drug. Subjects in this population will be used for demographic and safety summaries. Subjects in this population will be analyzed according to the drug received (actual drug concentration).

5.2 Pharmacokinetic Population

The PK population will include all subjects who receive at least 1 dose of moxidectin and provide an adequate number of blood samples for the determination of plasma PK parameters. Subjects in this population will be used for all PK summaries. Subjects in this population will be analyzed according to the drug received (actual drug concentration).

5.3 Electrocardiogram Population

The ECG population will include all subjects who receive at least 1 dose of study drug and have at least 1 pair of predose and postdose QTc data for at least 1 time point. Subjects in this population will be used for all digital ECG summaries and analyses. Subjects in this population will be analyzed as randomized.

5.4 Pharmacokinetic/Pharmacodynamic Population

The PK/PD population will include all subjects in the ECG population who have time-matched plasma concentrations for the active moxidectin treatments. Subjects in this population will be analyzed according to the drug received (actual drug concentration).

5.5 Handling of Missing Data

Missing data will not be imputed, except in the case of missing dates or times, for which values will be imputed if needed for analysis (ie, use of nominal time point value if elapsed time is missing). Data that are excluded from the descriptive or inferential analyses will be included in the data listings. This will include those measurements from excluded subjects, or measurements from unscheduled collections or extra measurements that may arise from 2 or more analyses of the plasma sample from the same time point.

In calculation of the concentration summaries and display in graphs, if values are below the quantitation limit (BQL) they will be set to zero; however, they will be presented as BQL in data listings. If all concentrations at a given time point are BQL, the mean will be presented as zero and the SD and percent coefficient of variation (CV%) will be reported as not applicable. If a mean concentration is BQL, it will be flagged in the summary table. For the calculation of PK parameters, BQL values that occur before dose administration will be set to zero. The BQL values that occur after dose administration, but before the first measurable concentration will be set to zero. If a BQL value occurs at the end of the collection interval (after the last quantifiable concentration) it will be treated as missing data. If 2 BQL values occur in succession after C_{max} , the profile will be deemed to have terminated at the first BQL value and any subsequent concentrations will

be omitted from the PK calculations.

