7 PHARMACOKINETIC ANALYSES

7.1 Moxidectin and Metabolite Concentrations

Moxidectin concentrations in plasma will be collected and analyzed for all subjects. Moxidectin concentrations in urine and feces and metabolite concentrations in plasma and urine will be analyzed for the subset of subjects who receive the 8-mg dose (See Table 3).

Table 3. Analyses for Each Matrix

Matrix	Analysis for moxidectin	Analysis for moxidectin metabolites
Plasma	✓ ^a	✓ ^b
Urine	✓ ^b	✓ ^b
Feces	✓ ^b	not analyzed

^a All subjects ^b 8-mg cohort

For plasma, the time course of concentrations of moxidectin will be presented and summarized using descriptive statistics (n, mean, SD, CV%, median, minimum, maximum, geometric mean, and geometric CV%) by time point and treatment. For urine and feces, the amount of moxidectin excreted by collection interval will be presented and summarized using descriptive statistics (n, mean, SD, CV%, median, minimum, maximum, geometric mean, and geometric CV%) by time point and treatment.

For plasma and urine, amount of metabolite by collection interval and metabolite to parent (molar equivalents) ratios will be presented and summarized using descriptive statistics (n, mean, SD, CV%, median, minimum, maximum, geometric mean, and geometric CV%) by collection interval and treatment.

Concentrations that are BQL will be treated as outlined in Section 5.5. Mean plasma concentration-time profiles will be plotted by treatment on linear and semilogarithmic scales using nominal times. Individual concentration-time plots and spaghetti plots with subject concentration-time profiles overlaid by respective treatments will be included in the appendices using linear and semilogarithmic scales.

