All subjects in the PK population will be included in the descriptive statistics for the PK parameters. No value for λ_z, AUC_{0-inf}, AUC_{ext}, CL/F, V_d/F, or t_{1/2} will be reported for cases that do not exhibit a terminal log-linear phase in the concentration-time profile. No PK parameters will be calculated for subjects with fewer than 4 quantifiable concentrations following BQL imputation. Additional PK parameters may be calculated, as necessary, to fully characterize the PK profile of moxidectin.

The PK parameters for urine moxidectin will be estimated as follows (data permitting):

$Ae_{urine(0-72)}$:	Urinary recovery between 0 and 72 hours, where $Ae_{(0-t)} = \sum_{n=1}^t (C_{urine,i} * V_{urine,i})$, where $C_{urine,i}$ represents the concentration of drug in urine during collection interval i, and $V_{urine,i}$ represents the cumulative urine volume during collection interval i.
$Ae_{urine(0-24)}$:	Urinary recovery between 0 and 24 hours, where $Ae_{(0-24)} = C_{urine(0-24)} * V_{urine(0-24)}$.
$Ae_{urine(24-48)}$:	Urinary recovery between 24 and 48 hours, where $Ae_{(24-48)} = C_{urine(24-48)} * V_{urine(24-48)}$.
$Ae_{urine(48-72)}$:	Urinary recovery between 48 and 72 hours, where $Ae_{(48-72)} = C_{urine(48-72)} * V_{urine(48-72)}$.
$CL_{r(0-72)}$:	Renal clearance from 0 to 72 hours, where $Ae_{(0-72)}/AUC_{(0-72)}$.
$CL_{r(0-24)}$:	Renal clearance from 0 to 24 hours, where $Ae_{(0-24)}/AUC_{(0-24)}$.
$CL_{r(24-48)}$:	Renal clearance from 24 to 48 hours, where $Ae_{(24-48)}/AUC_{(24-48)}$.
$CL_{r(48-72)}$:	Renal clearance from 48 to 72 hours, where $Ae_{(48-72)}/AUC_{(48-72)}$.

The PK parameters for feces moxidectin will be estimated as follows (data permitting):

$Ae_{feces(0-72)}$:	Fecal recovery between 0 and 72 hours, where $Ae_{(0-t)} = \sum_{n=1}^t (C_{feces,i} * W_{feces,i})$, where $C_{feces,i}$ represents the concentration of drug in feces (ng/g) during collection interval i, and $W_{feces,i}$ represents the total fecal mass during collection interval i.
$Ae_{feces(0-24)}$:	Fecal recovery between 0 and 24 hours, where $Ae_{(0-24)} = C_{feces(0-24)} * W_{feces(0-24)}$.
$Ae_{feces(24-48)}$:	Fecal recovery between 24 and 48 hours, where $Ae_{(24-48)} = C_{feces(24-48)} * W_{feces(24-48)}$.
$Ae_{feces(48-72)}$:	Fecal recovery between 48 and 72 hours, where $Ae_{(48-72)} = C_{feces(48-72)} * W_{feces(48-72)}$.

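### The trailing-BQL rule for PK parameters is not limited to plasma, so a late urine or feces interval that is BQL drops out of Ae and CLr instead of counting as about zero

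*SAP*

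**What the plan says.** SAP Section 5.5 handles BQL values according to their use.

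- For summaries and figures: "In calculation of the concentration summaries and display in graphs, if values are below the quantitation limit (BQL) they will be set to zero". Position in the profile does not matter.
- For PK parameters, early values: "The BQL values that occur after dose administration, but before the first measurable concentration will be set to zero".
- For PK parameters, late values: if a BQL value falls "after the last quantifiable concentration) it will be treated as missing data". Two successive BQL values after Cmax also end the profile.
- On missing values in general: "Missing data will not be imputed, except in the case of missing dates or times".

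Section 7.1 describes moxidectin in plasma, urine and feces, and metabolites in plasma and urine, and then states: "Concentrations that are BQL will be treated as outlined in Section 5.5". It does not restrict this to one matrix.

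Section 7.2 lists urine and feces Ae, and CLr, as PK parameters. Ae in an interval is concentration times urine volume, or times W, where W "represents the total fecal mass during collection interval i". CLr is Ae divided by the plasma AUC of the same interval. No separate BQL rule is given for these parameters. Urine and feces are analyzed only in the 8-mg cohort (n = 10), in three postdose pools: 0-24, 24-48 and 48-72 hours (Section 3.3, Table 2 footnotes g and h).

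**The concern.** Treating a trailing BQL value as missing suits a plasma curve, where it stops an unmeasurable tail from distorting AUC and the terminal slope. A pooled excretion interval is different. A BQL result on a 48-72 hour pool is a measurement: the amount excreted was at least zero and below LLOQ x volume (or mass). Calling it missing discards that information selectively, because only subjects with low late excretion are removed. The remaining mean describes those who still had measurable drug.

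The rule is also inconsistent. One laboratory result counts as zero before the first measurable value and vanishes after the last. If the zero rule for summaries and graphs covers the amount-excreted figures (14.2.1.6 and 14.2.1.9), while the parameter rule covers the urine and feces tables (14.2.1.3 and 14.2.1.4), the report can show different means for the same interval. At stake is how much moxidectin appears to be recovered late in the collection period, in a cohort of 10.

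**Working it through.** The SAP states no excretion figure, LLOQ or expected BQL rate, so there is no planned number to reproduce.

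**Inputs.** n = 10 (Section 3.3). k is the number of subjects whose 48-72 h pool is BQL after an earlier quantifiable pool; it is an assumption, shown over a range. Subjects with no quantifiable pool are not in k: the rule for values before the first measurable concentration arguably makes them zero.

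**Late-interval mean.** Let S be the sum of Ae(48-72) over the subjects who are not dropped.

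- BQL as missing: S/(10-k)
- BQL as zero: S/10
- Ratio: 10/(10-k)

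| k | Ratio |
|---|---|
| 1 | 10/9 = 1.11 |
| 2 | 10/8 = 1.25 |
| 3 | 10/7 = 1.43 |
| 5 | 10/5 = 2.0 |

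Ae(24-48) is affected in the same way when both later pools are BQL.

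**Renal clearance.** With Ae(48-72) = 0, CLr(48-72) = 0/AUC(48-72) = 0. Dropping the subject therefore raises the mean CLr as well. Against the BQL = 0 mean the factor is again 10/(10-k) if AUC(48-72) is available for all 10 subjects. Against the true mean it also depends on each subject's AUC.

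**Is zero a fair reference?** Measure amounts in units of LLOQ x volume. Assume that retained subjects average 2 units and that the true amount in a BQL pool is f units. The overstatement against the true mean is 2 / {[2(10-k) + f k]/10}.

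- f = 0.5: k=2 gives 2/1.70 = 1.18; k=5 gives 2/1.25 = 1.60.
- f = 1 (the limit): k=2 gives 2/1.80 = 1.11; k=5 gives 2/1.50 = 1.33.

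Under these assumptions the overstatement shrinks but remains.

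**Ae(0-72).** If the available intervals are summed, the dropped interval contributes nothing and the total equals the BQL = 0 total. If one missing interval makes the sum missing, affected subjects are lost. An illustrative log-normal simulation (assumed medians falling over the three intervals in the ratio 2.0 : 1.2 : 0.8; log-scale SD 0.5 between and 0.2 within subjects) gave, in units of LLOQ x volume:

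| Trailing BQL at 48-72 h | Never quantifiable | True mean Ae(0-72) | BQL = 0 or available intervals summed | Affected subjects lost |
|---|---|---|---|---|
| 19% | 1% | 9.23 | 9.04 | 10.34 |
| 56% | 10% | 4.63 | 3.87 | 5.57 |
| 60% | 26% | 3.24 | 2.19 | 2.21 |

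In the last row many subjects count as zero because they never have a quantifiable pool, and the mean falls below the true value. In that scenario mean Ae(48-72) under the current rule is 0.73 times the true mean, yet still 2.48 times the BQL = 0 mean.

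**The case against.** The strongest reply is that the trailing rule was meant for plasma. No sentence applies it by name to urine or feces, and the neighbouring text speaks of Cmax, a profile and the plasma sample. Section 7.2 also withholds all PK parameters from subjects with fewer than 4 quantifiable concentrations. Read across matrices, that would rule out every excretion parameter, since there are only three postdose pools. This is good evidence of intent. It does not settle the matter: Section 7.1 sends BQL values for all matrices to Section 5.5, and if Section 5.5 is plasma-only, Ae and CLr have no BQL rule. Either reading calls for the same correction.

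A second reply is that the Section 7.1 summaries of amount excreted, and the related figures, can be read under the zero rule. That stands. It confines the problem to the Section 7.2 Ae and CLr calculations, and it creates the possible mismatch between tables and figures.

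Three stronger readings are tempting but not supported:

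- A reader might infer that total 0-72 h recovery is overstated or lost for many subjects. The SAP does not say how a missing interval enters the sum. A BQL 0-24 h pool cannot be trailing in any case.
- A reader might infer that an interval without a stool is dropped as missing. The SAP does not say so. The wording that allows up to four fecal samples includes the predose specimen, so it need not foresee a postdose interval without stool, and a fecal mass of zero is a known quantity.
- A reader might infer that the whole excretion objective rests on these parameters. Urinary metabolite amounts and metabolite-to-parent ratios also inform it.

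**Conclusion.** The point holds for late-interval Ae and CLr. Followed literally, Section 5.5 turns a known, near-zero amount into a missing value and raises mean Ae(48-72) by 10/(10-k) relative to BQL = 0, with mean CLr(48-72) moving the same way. The formula is exact; k is assumed, and if no trailing BQL occurs there is no effect.

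The comparison is with a consistent BQL = 0 rule. Against the true mean the excess is smaller, and it can reverse if many subjects are never quantifiable. For Ae(0-72) the effect depends on a summing choice that the SAP leaves open.

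The importance is modest: exploratory excretion endpoints in one cohort of 10. The QT analysis does not use these parameters.

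**What to change.** In Section 5.5, limit the trailing-BQL and two-successive-BQL rules to plasma concentration-time profiles. In Section 7.2, state that a urine or feces interval with a BQL concentration has zero amount for Ae and CLr, whatever its position, so that tables and figures agree. While editing, say how Ae(0-72) is formed when an interval was truly not collected.

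This costs a few sentences and no new data. The price is somewhat lower reported late-interval recoveries, and zero slightly understates an amount that lies anywhere below LLOQ x volume or mass. Section 3.5 defers the urine and feces analyses until after Period 2, but the change should be made before the Day 22 unblinding so that it remains a priori under Section 4.
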